6.5 Inclusion of Vulnerable Subjects

Inclusion of Pregnant Women, fetuses or neonates

Not applicable.

6.6 Lifestyle Considerations

Not applicable

6.7 Screen Failures

Study eligibility is based entirely on clinical records and medically indicated imaging studies.

Subjects consent to participate in the study before undergoing any study-specific activity.

Subjects are classified as screen failures if they undergo study-specific catheterization but NOT an attempt at BASILICA using the TELLTALE guidewire system.

Baseline data acquired for screen failures are retained to facilitate reporting of screen failure participants, to meet the Consolidated Standards of Reporting Trials (CONSORT) publishing requirements and to respond to queries from regulatory authorities.

In case of attempted but unsuccessful TELLTALE BASILICA-TAVR leaflet traversal or laceration, subjects are followed for 30 days to assure freedom from screening- or procedure-related adverse events.

Subjects are eligible for repeat screening and enrollment, in which case they are assigned new subject specific identifying numbers (SSPIN).

6.8 Strategies for Recruitment and Retention

Subjects will be recruited from the Structural Heart Disease clinical programs of the participating medical centers.

We expect to accrue at least one subject per month per site from among enrollment centers. There is no subject enrollment at NIH Clinical Center.

The distribution of planned enrolling sites assures accessibility of the trial to ethnically, racially, economically, and geographically diverse populations. The study will track sex, age, ethnicity, and racial background of subjects.

Once recruited, subject retention rate is expected to be high because follow-up activities are not onerous and are timed to correspond with routine follow-up medical care.

Costs

Subjects are responsible for the costs of medical care associated with participating in this protocol.

NHLBI is the Sponsor, which automatically qualifies sites for CMS reimbursement for costs of research-related medical care, according to the CMS Clinical Trial Program (CTP), for CMS beneficiaries. The CTP policy is described on

<https://www.cms.gov/Medicare/Coverage/ClinicalTrialPolicies/index.html>.

The result is that CMS is “explicitly authorize[d to provide] payment for routine patient care costs...and costs due to medical complications associated with participation in clinical trials.”

The TELLTALE system test articles are provided without cost by the manufacturer, Transmural Systems.

Compensation

Candidates and subjects receive no compensation for screening or for participating in this study.

7 STUDY INTERVENTION

7.1 Test articles and Indications for Use

Device Description

Based on the clinical learnings from the NIH-sponsored BASILICA IDE with off-label/off-shelf devices, Transmural Systems collaborated with [name] at the NIH and principal site investigators of the IDE (Drs. [name], [name], [name] and [name]) to design the TELLTALE Electrosurgical Guidewire System, providing more reliable devices for the procedure.

The TELLTALE Electrosurgical Guidewire System is comprised of the TELLTALE Guidewire and accessories to aid with the preparation, placement and use of the guidewire. The System includes:

- TELLTALE Guidewire
- TELLTALE Accessories
 - Spring-loaded connector cable
 - Guide catheters (for left coronary cusp and for right coronary cusp)
 - Insulation Envelope
 - Insulation Tube
 - Denuder/Kinker
 - Guidewire grippers

Indications for Use

The TELLTALE Electrosurgical Guidewire System is indicated for transcatheter electrosurgical traversal and laceration of native and bioprosthetic tissue in patients at risk of coronary obstruction during TAVR.

System Components

TELLTALE Guidewire

The TELLTALE Guidewire has an outer diameter of 0.014" and a working length of 310cm (Figure 5). It is composed of a 304V stainless steel guidewire covered with an outer insulative layer. The distal tip and proximal end of the guidewire are uninsulated. The TELLTALE Guidewire mid-shaft is provided to the user fully insulated to protect the operator from RF energy when the uninsulated guidewire tip is used for electrosurgical leaflet traversal inside the patient (Figure 5).

The proximal end of the TELLTALE Guidewire, which has no patient contact, is uninsulated and gold-plated to allow for connection to an electrosurgery generator to facilitate the delivery of monopolar RF energy to the cutting surfaces of the device.

There are two cutting surfaces of the TELLTALE Guidewire.

- 1) the distal tip for leaflet traversal
- 2) a mid-shaft cutting location for leaflet laceration (approximately 160cm from the distal tip).

The mid-shaft of the TELLTALE guidewire is identified by a 10mm gold marker band which is radiopaque. The mid-shaft cutting surface is created by the user by removing the insulative coating (denuded) after the distal tip is used to traverse through tissue. Therefore, the mid-shaft cutting surface does not contact the patient during electrosurgery using the distal tip. When used for the BASILICA procedure, the distal tip does not contact the patient during electrosurgery when RF energy is turned on for use at the mid-shaft cutting location.

The TELLTALE Guidewire design and procedure outlined in the Instructions for Use (IFU) will ensure that the non-insulated portions of the wire are only in contact with the patient in an intentional way during the procedure.

[figure not shown]

Figure 5. Image of TELLTALE Guidewire with cross section of the denuded area (prior to kinking). The insulative outer layer of the guidewire is clear but is represented in figure 4 with the gray color.

TELLTALE System Accessories:

- Spring Loaded Connector (Figure 6): A detachable spring-loaded connector cable that plugs into the RF generator and allows for a secure insulative connection between the TELLTALE Guidewire and the generator. The detachable connector allows for exchange of catheters over the TELLTALE Guidewire as needed during the procedure.
- Transmural *Pachyderm* Guide catheters (Figure 7): The guide catheters are specifically shaped to aid in leaflet traversal by allowing physicians to select the traversal location and providing backup support for TELLTALE Guidewire leaflet traversal.
- Insulation Envelope (Figure 8): The insulation envelope is only used during the traversal procedure. It is provided as an added layer of insulation to protect the user and patient from un-intended RF energy.
- Insulation Tube: The insulation tube is a plastic tube provided for use during laceration of the leaflet only. It is provided as an insulated cover for the denuded distal tip of the guidewire to protect the user and patient from un-intended RF energy.

[figure not shown]

Figure 6. Image of Spring-loaded connector cable for connection to RF Generator

Figure 7. Image of Transmural *Pachyderm* Guide Catheters for the left and right coronary cusps, respectively

Figure 8. Image of Insulation Envelope

- Denuder/Kinker (Figure 9): The Denuder/kinker is provided to (1) create a reproducible denuded, or uninsulated, area at the mid-shaft location of the TELLTALE Guidewire for laceration and (2) kink the TELLTALE Guidewire at the lacerating surface to produce the required angle for the BASILICA procedure.

[figure not shown]

Figure 9. Image of Denuder and kinker. (Left) Open position, (Middle) Closed position, (Right) Denuded and Kinked guidewire

- Guidewire gripper (Figure 10): The guidewire gripper is attached to a standard Y-adaptor and clamps onto the TELLTALE Guidewire to assist with guidewire traction during the procedure.

[figure not shown]

Figure 10. Image of Guidewire Grippers (Left) Open position, (Right) Closed position

The generator connector cable, gripper insulation envelope, insulation tube, and denuder/kinker are non-patient contact parts and are constructed of standard medical materials.

7.2 BASILICA-TAVR using the TELLTALE System

Study Intervention Description

Candidates will be identified by the participating structural heart disease programs. In evaluation of aortic valve disease, candidates will undergo clinical evaluation, echocardiography, optional coronary arteriography, and contrast-enhanced gated cardiac CT. Eligibility will be reviewed and proposed by the local multidisciplinary heart teams. Candidates will then undergo central eligibility review by the sponsor and designated investigators. If deemed eligible, candidates will be offered participation in the study.

Once enrolled, subjects will undergo baseline assessment and blood tests.

Subjects will be admitted to the hospital and undergo TAVR with BASILICA using the Transmural TELLTALE guidewire system. They will undergo primary endpoint assessment before discharge.

The TELLTALE BASILICA-TAVR procedure is planned from a contrast-enhanced CT of the heart to select a suitable transcatheter heart valve size, predict suitability of the sub- and supra-annular

landing zone, and predict post-TAVR coronary obstruction related leaflet encroachment on the sinotubular junction and coronary artery ostia. Knowledge of the aortic valve operative history is integrated into this assessment. These data are used to select a BASILICA traversal point, radiographic landmarks, and fluoroscopic projection angles.

The procedure is performed under general anesthesia or under moderate sedation at the discretion of the institutional heart team. The TELLTALE BASILICA procedure has five steps: (1) engagement of the target leaflet with a guiding catheter and optional commercial deflectable guiding sheath; (2) electrosurgical leaflet traversal with the TELLTALE guidewire, (3) preparation and positioning of the TELLTALE guidewire electrosurgical leaflet laceration surface; (4) electrosurgical leaflet laceration with the TELLTALE guidewire, immediately followed by (5) TAVR. These are all guided by fluoroscopy, with adjunctive echocardiography as needed.

Research study participation is defined as beginning the moment BASILICA traversal is attempted. This is in case TAVR is found not to be indicated at the time of the index invasive procedure, or in case BASILICA guidewire traversal is not otherwise attempted.

First catheter access is obtained typically via two arterial introducer sheaths (one for hemodynamics and angiography, one for TAVR, both also used for BASILICA) and at least one venous introducer sheath for temporary transvenous pacing. Large hydraulic-hub introducer sheaths may allow multiple guiding catheters to be introduced via a smaller number of arterial access sites. Anticoagulation with heparin or equivalent achieves an activated clotting time > 300s.

Hemodynamic and echocardiography measurements are recorded at baseline including gradients across the aortic valve, severity of valvular obstruction and severity of valvular regurgitation.

Two retrograde catheters are positioned, using a guidewire anchor as needed, in the LVOT and aorta respectively. Care is taken to avoid entrapment of mitral valvular structures. A snare catheter is positioned in the LVOT. A TELLTALE system guiding catheter, with- or without- a tandem coaxial catheter or microcatheter, directs the TELLTALE electrosurgery guidewire, against the base of the coronary cusp targeted for laceration, using fluoroscopic and/or echocardiographic guidance. Alternative guiding catheters are employed as described in the TELLTALE Instructions for Use.

Leaflet traversal is accomplished by transcatheter electrosurgery by connecting the TELLTALE.014" guidewire to an electrosurgery generator during a short burst of "pure, cutting" radiofrequency energy at approximately 10-30W as required. The guidewire is repositioned as needed until it crosses the aortic leaflet and is snare-retrieved and externalized. Nonionic flush (dextrose 5%) can be administered as needed via the guiding catheters to reduce guidewire char and thromboembolism.

Operators are encouraged to perform contrast angiography through the traversal guiding catheter to demonstrate position of TELLTALE guidewire traversal.

Next the TELLTALE guidewire is appropriately kinked and denuded to prepare the leaflet laceration surface, which is positioned across the intended valve leaflet.

A left ventricular pigtail catheter, with or without guidewire, may be positioned before or after the laceration step, at operator discretion.

Transcatheter cerebral embolic protection devices are employed at operator discretion.

Next TELLTALE BASILICA is accomplished by electrosurgical laceration during nonionic flush and traction on the TELLTALE guidewire. Electrosurgery is applied in short bursts until laceration is successful and complete, as evidenced by free withdrawal of the guidewire.

Hemodynamics are recorded quickly after laceration before TAVR. Predilatation, including intentional disruption of the bioprosthetic valve frame, is performed at operator discretion, before or after TAVR. Then TAVR is performed using established techniques typically during rapid ventricular pacing. The device size and inflation volumes are selected and applied at the discretion of the operator. Post-dilatation is performed at operator discretion to achieve an optimum TAVR result.

Coronary artery patency, and access through TAVR device struts, is established using selective coronary angiography.

Completion hemodynamics and echocardiography are recorded. Finally, percutaneous arterial and venous vascular hemostasis is obtained and the subject convalesces in the appropriate inpatient recovery unit.

Before discharge, follow-up transthoracic echocardiography is recorded. Clinically-indicated blood test results are recorded for research. These are repeated at 30 days.

Anticoagulation and antiplatelet therapy is prescribed after discharge at the physicians' discretion, and is recorded.

All subjects are to be enrolled in the TTV-Registry post-marketing TAVR registry.

Subjects would receive continuing care from their primary physicians and/or cardiologists with consultant input as requested from the structural heart disease program.

Subjects may undergo a post-TAVR medically-indicated contrast-enhanced CT at their physicians' discretion, in which case NHLBI requests to receive and analyze the images.

Subjects' participation in the study concludes at the 90 days follow-up and termination visit.

Study duration

Subjects participate through the 90 days follow-up and termination visit.

We aim to complete the study in 12 months for enrollment + follow-up.

Number of enrollment sites

Up to 15 sites will enroll and treat subjects in this study.

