3.3 Risk/Benefit Assessment

Known Potential Risks (Anticipated Adverse Device Effects)

TELLTALE/BASILICA-specific complications

- Embolization of air, valve debris, atheroma, or thrombus/clot to coronary, cerebral, visceral, or systemic circulation possibly causing symptomatic ischemia/infarction
- Myocardial ischemia or infarction (acute coronary syndrome or heart attack)
- Aortic regurgitation after laceration before TAVR, possibly causing hypotension or cardiogenic shock
- Avulsion or other injury of the native or prosthetic aortic valve leaflet, including leaflet prolapse into the coronary arteries, and including embolism of the leaflet into the coronary, cerebral, visceral, or other systemic arteries
- Inadvertent injury of the mitral valve apparatus requiring transcatheter or surgical repair
- Traversal into the left atrium or other non-target chamber
- Electrical coupling of TELLTALE guidewire and (a) bioprosthetic valve frame, (b) guiding catheters, (c) guidewires and snares causing heating, thromboembolism, tachyarrhythmia, and electrosurgery failure
- Native coronary artery injury from mechanical or electrosurgery injury requiring percutaneous catheter or surgical treatment
- Other arterial perforation or injury or dissection, including requiring surgical treatment
- Failure to engage the intended native or bioprosthetic aortic valve leaflet with TELLTALE system to initiate traversal at the intended location
- Mechanical failure of the TELLTALE Guidewire System including fracture and embolization of the guidewire or of the delivery catheters
- Stroke or transient ischemic attack or paralysis
- Permanent disability
- Death

General complications of TAVR and BASILICA-TAVR catheter procedure including TELLTALE system

- BASILICA failure: Failure to prevent coronary obstruction and acute myocardial ischemia requiring transcatheter therapy including percutaneous coronary stenting in a heterotopic ("snorkel") or orthotopic (through TAVR struts) position, or requiring emergency cardiac surgery repair
- BASILICA failure: coronary obstruction caused by the malorientation of struts of TAVR device, or by fabric skirt of TAVR device, despite successful leaflet laceration
- Hypotension or shock or cardiopulmonary arrest including requiring cardiopulmonary resuscitation, chest compressions, cardioversion/defibrillation, vasoactive medications, and/or mechanical circulatory support and/or extracorporeal membrane oxygenation

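### The point at which a subject starts to count is not fixed: section 7.2 uses attempted traversal, other sections use an undefined attempt, and sections 10.3 and 10.4 name different primary sets

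*Combined protocol and SAP*

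**What the plan says.** Section 7.2 sets the start point: "Research study participation is defined as beginning the moment BASILICA traversal is attempted". Its stated purpose is to deal with TAVR being found not indicated at the index procedure, "or in case BASILICA guidewire traversal is not otherwise attempted". The same section has already called people enrolled before the procedure: "Once enrolled, subjects will undergo baseline assessment and blood tests".

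Section 7.2 also lists five steps. The first is "engagement of the target leaflet with a guiding catheter and optional commercial deflectable guiding sheath"; electrosurgical traversal is the second. Section 7.1 includes "Guide catheters (for left coronary cusp and for right coronary cusp") among the accessories of the TELLTALE System. Section 3.3 lists as a TELLTALE-specific complication "Failure to engage the intended native or bioprosthetic aortic valve leaflet with TELLTALE system to initiate traversal at the intended location".

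Section 6.7 gives the exclusion rule: "Subjects are classified as screen failures if they undergo study-specific catheterization but NOT an attempt at BASILICA using the TELLTALE guidewire system". It speaks of keeping baseline data for screen failures and allows repeat screening and enrolment under a new identifier.

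Section 9.4 starts adverse event recording at an attempt at the procedure, and 10.2 accrues until 90 subjects have had one. Section 10.3 describes a per-protocol analysis of attempted subjects. Section 10.4 makes the primary analysis intention-to-treat in all study subjects. No section defines an attempt.

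**The concern.** The study is single-arm and reports proportions with confidence intervals. Membership of the denominator should not depend on how the first device step ended. Between introduction of a TELLTALE component and a traversal attempt there is a stretch of device exposure that section 7.2 places before participation. Section 3.3 foresees failure in that stretch, and its list of device risks also contains "Stroke or transient ischemic attack or paralysis", which is a component of the primary safety endpoint in 4.5.

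If 7.2 governs, a subject stopped in that stretch can leave the analysis, and accrual continues until another subject fills the place. For efficacy the omission works in one direction only: nobody without a traversal attempt can be a success, so leaving such subjects out can only favour the device. For safety, an event in such a subject would be missing from the primary proportion. Under 6.7 the same person could also return with a new identifier and be counted only for the second procedure.

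**Working it through.** **1. What each section counts.**

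| Section | Use | Trigger |
|---|---|---|
| 6.7 | Screen failure or not | Attempt at BASILICA with the TELLTALE guidewire system |
| 7.2 | Start of participation | Attempt at traversal (step 2) |
| 8.2 | Follow-up after an abort | Aborted procedure without laceration |
| 9.4 | Start of adverse event recording | Attempt at the TELLTALE BASILICA-TAVR procedure |
| 10.2 | Count to 90 | Attempted TELLTALE BASILICA-TAVR |
| 10.3 | Analysis cohort | Attempt at TELLTALE BASILICA-TAVR, per-protocol |
| 10.4 | Primary analysis | Intention-to-treat, all study subjects |

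**2. One subject under two readings.** Suppose a TELLTALE guide is introduced, the leaflet cannot be engaged, and the procedure stops.
- *Attempt means traversal (7.2):* screen failure under 6.7, not counted in 10.2, outside 10.3. Under 10.4 the subject is in or out depending on whether a study subject is someone enrolled or someone participating.
- *Attempt means the procedure or the system:* step 1 is already part of the procedure, so the subject is counted, recorded and analysed.

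Under 4.4 a retained subject is a non-success. Only the traversal component is qualified by whether it was attempted; laceration is required without that qualification.

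**3. The plan's own probability.** Section 10.2 relays a figure of more than 80% for seeing at least one stroke in 60 bioprosthetic subjects at 2 × 1.4% = 2.8%. Check: 1 − (1 − 0.028)^60 = 0.818. It reproduces. It does not measure the effect of the definition.

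**4. Size, as illustration only.** The documents give no count of such subjects, so k is assumed. Section 10.4 names no interval method; exact (Clopper-Pearson) 95% limits are used here. With n successes in n, the lower limit is 0.025^(1/n); for 90/90 this is 0.025^(1/90) = 0.960.

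Efficacy, assuming every traversal-attempted subject succeeds:

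| Case | Result | 95% CI |
|---|---|---|
| k left out | 90/90 = 100% | 96.0–100 |
| k = 1, reclassified retrospectively | 90/91 = 98.9% | 94.0–100.0 |
| k = 1, counted within the 90 | 89/90 = 98.9% | 94.0–100.0 |
| k = 2, reclassified retrospectively | 90/92 = 97.8% | 92.4–99.7 |
| k = 3, reclassified retrospectively | 90/93 = 96.8% | 90.9–99.3 |

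Safety, assuming no events in the 90 counted: 0/90 = 0% (0–4.0). If one left-out subject had an event, retrospective reclassification gives 1/91 = 1.1% (0.03–6.0), and prospective counting gives 1/90 = 1.1% (0.03–6.0).

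Each such subject is worth about one percentage point. The first lowers the efficacy limit by about two points (96.0 to 94.0).

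**The case against.** The strongest reply is that only 7.2 speaks of traversal. Sections 6.7, 9.4, 10.2 and 10.3 refer to the system or the procedure, engagement is step 1 of that procedure, and the guides belong to the system. Nothing in section 10 points back to 7.2. On this natural reading the subject is already retained. That stands as a reading, but the documents do not say that it prevails, and 7.2 contains the only explicit start point.

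A reader might infer that a stroke or coronary injury during engagement would go unreported. The documents do not support that. Section 8.2 requires at least 30 days of follow-up after a procedure aborted without laceration, and on its face this can include a stop before traversal. Appendix B (14.2) requires sites to report serious adverse events, anticipated device effects and deaths to the sponsor, and the adverse device effect definition in 9.4 carries no traversal condition.

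A reader might also take the interim report in 3.2, with 15 native subjects consented and 14 treated, as an instance of the problem. That analysis was triggered by the fifteenth consent, so a lag before treatment explains the gap equally well.

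The number of cases is hypothetical. Section 7.2 allows alternative guiding catheters, so step 1 does not always involve a TELLTALE guide. Section 3.2 counts difficulty in positioning against the leaflet as inability to traverse, which is already a non-success. The efficacy endpoint in 4.4 is confined to the guidewire. All of this limits the size. The 10.3/10.4 conflict is a separate defect that stands without the engagement scenario; it matters here because it leaves the ambiguity unresolved.

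**Conclusion.** The point holds as an ambiguity in who is counted. Section 7.2 and the procedure-level sections can place the same device-exposed subject outside or inside the primary set, and 10.3 and 10.4 do not settle which. The exposure is the analysis denominator, chiefly for the primary safety endpoint, and not unreported harm. Exclusion is possible, not certain: the plan does not use the word replacement or name a separate safety set, and both follow only from reading 10.2, 9.4 and 10.3 in the light of 7.2.

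The effect is about one percentage point per subject, in the device's favour for efficacy, and it is zero if no such subject occurs. This rests on an assumed number of cases and on each being a non-success under 4.4. Severity is minor to moderate. No figure in the plan is wrong on this account.

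**What to change.** 1. Define an attempt once, as first introduction of any TELLTALE System component into the body with intent to perform BASILICA. Use that definition in 6.7, 7.2, 8.2, 9.4 and 10.3 for adverse event recording and the primary safety set. If TAVR is found not indicated before any component is introduced, the subject remains a screen failure, which preserves that purpose of 7.2.
2. Replace the competing labels in 10.3 and 10.4 with this one named primary set.
3. Leave the endpoint in 4.4 unchanged, and also report it in traversal-attempted subjects so that both denominators are visible.
4. List every catheterised subject without an attempt, with the reason and any event. This extends the screen-failure reporting that 6.7 already intends.
5. Open-label results have been seen (3.2, interim analysis for Amendment B). Date the change, leave the accrual count for subjects already enrolled as it is, and report results under both definitions.

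The cost is wording in the sections named, one extra denominator and one listing. The reported rate may be slightly less favourable. Follow-up of earlier screen failures may be incomplete and should be described as such.
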